### **Intervention Assignment and Recruitment**

The educational intervention was integrated into the residency programs in IM and FM, and into the curriculum for DNP students. We initially aimed to enroll entire specialty cohorts of IM, FM, and NP trainees over a 3-year period, with each academic year constituting an intervention cycle, with 3 cycles of implementation corresponding to 3 sequential academic years. Due to the COVID emergency, this was extended to 4 years of enrollment across 4 academic years. Within the first pre-COVID academic year, we randomized training times to 1 of 5 start dates using a stepped wedge design. Our biostatistician used a random sequence generator to assign 5 groups of learners, from within each program, to 1 of 5 staggered intervention training dates within an academic year.

**Version 3.0 updates:** Due to COVID, randomization to training times within each academic year was not possible. Each training program schedulers assigned the trainees according to availability within the learning schedules in order to maintain clinician availability to provide care during the COVID crisis. However, across all years, the program was delivered over two in-person sessions (and via virtual teleconferencing during COVID), scheduled five weeks apart, to leverage a spaced learning design.

The sessions were designed to minimize the time burden of the intervention on trainees outside of the classroom. As such, the in-person training sessions combined multiple educational components that trainees completed individually, but as part of an onsite group session. In each educational session, components included: “individual” online didactic modules, online IATs, face-to-face clinical practice simulation with SPs, and “group-based” facilitated debriefing sessions. Originally, training in skills to mitigate the effects of implicit bias detailed by Devine et

al. was addressed as part of the group-based IAT debriefings that preceded case simulations with SPs. Each of the two, in-person sessions lasted about four hours. If trainee participants were unable to attend one of the sessions due to scheduling conflicts, we provided alternative dates for attendance.

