## **Statistical analysis**

**Version 3.0 updates:** To maintain clinical staff services in the hospital, we were not able to maintain the cluster randomized stepped wedge design of training role out to all clinics and cohort during the COVID emergency. Therefore, we analyze these data as cohort study.

The first step of statistical analysis was examining the distribution of all data points to identify outliers or errors in the data of primary interest. Unadjusted analysis of categorical data was conducted with chi-square tests; analysis of continuous data used analysis of variance. Mixed effects regression models were fit to estimate the relative changes of clinical outcomes (BP values and clinical cut points) for patients seen by residents in the 6 months before and 6 months following the intervention periods. Mixed-effect linear regression models (logit models for normal and optimal BP categories) were fit with mixed effects for resident ID and for study cohort. All mixed-effect models also contained terms for the additional terms to account for study composition and potential confounders: study population (race and insurance strata),

clinical department (Family Medicine vs Medicine), age and sex, and relevant clinical comorbidity(diabetes, obesity, hyperlipidemia, coronary artery disease, cerebrovascular disease, and tobacco use). In order to determine if the study intervention was differentially effective for the different patient groups (ie. white patients with Medicaid and patients of color with either private insurance, Medicare, or Medicaid), we modeled interaction terms between 4-level population variable and intervention period. P-values less than 0.05 were considered statistically significant.

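### Training was delivered in groups, but the model has no training-group-by-period term; if before/after changes are correlated within groups, the standard error is too small

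*Combined protocol and SAP*

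**What the plan says.** **Assignment.** Under Intervention Assignment and Recruitment, the biostatistician "used a random sequence generator to assign 5 groups of learners, from within each program, to 1 of 5 staggered intervention training dates". This covers year 1 only: "Within the first pre-COVID academic year, we randomized training times to 1 of 5 start dates using a stepped wedge design". The Version 3.0 update in the same section says that afterwards "Each training program schedulers assigned the trainees according to availability within the learning schedules".

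**Delivery.** The same section describes two sessions five weeks apart in every year, held virtually during COVID. They combined components "that trainees completed individually, but as part of an onsite group session" with group debriefings led by a facilitator. Trainees who could not attend a session were offered another date.

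**Analysis.** The Statistical analysis section states: "Therefore, we analyze these data as cohort study". It compares patients seen before and after training with mixed-effect models that "were fit with mixed effects for resident ID and for study cohort". Adjustment terms cover race and insurance strata, department, age, sex and comorbidity. No training group, session, start date or calendar-time term is named, and the only interaction with period is with the patient population variable. Study cohort is not defined. Elsewhere the document declares clustering only of patients within trainees.

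**The concern.** Trainees in one session share its content, its format (in person or virtual) and roughly the same before and after windows. The content was redesigned after year 1, and COVID disrupted both delivery and scheduling. It is therefore plausible that the before/after change in blood pressure is more alike among patients of trainees from one session than among patients of trainees from different sessions.

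A resident effect removes stable differences between residents. It does not represent a change that a whole group shares. If such shared change exists, the model counts residents of one group as independent evidence about the training effect. Its confidence interval is then too narrow, and the 0.05 threshold is crossed too often on the primary outcome.

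**Working it through.** **The plan's own figure.** The Sample size calculation section claims more than 90% power for a 3 mmHg difference but gives no SD, intraclass correlation or design effect, so the figure cannot be reproduced. With independent readings and a two-sided 0.05 test (sidedness is not stated), it holds for any SD up to about 34 mmHg with 2050 and 4100 readings, and up to about 24 mmHg with the 1025 and 2050 readings for uncontrolled hypertension. At SD 20 the power is 99.98% and 97.5%. The claim is plausible, but no clustering is stated in it.

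**Which omitted term matters.** Each trainee is meant to have readings before and after training, so a stable group difference cancels in the contrast. A generalised least squares check confirms this (102 residents, 8 or 23 groups, unbalanced counts, SD 18, resident share of variance 3%, group share 2%):

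- No group-by-period variance: SE 0.682 from the resident-only model and 0.681 with a group intercept. Omitting the intercept does no harm.
- 1% of variance at group-by-period level: the resident-only model reports 0.681 (8 groups) or 0.679 (23 groups), while the true SE of its estimate is 1.129 or 0.878.

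**Size on the plan's readings.**

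- From the plan: 2050 readings before, 4100 after.
- Assumed: SD 20 mmHg; group-by-period SD s from 0 to 2 mmHg; equal-sized groups.
- Assumed number of groups G: 60 (5 dates × 3 programmes × 4 years), or 20 if programmes sharing a date move together (5 × 4).

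Variance without the group term: 400 × (1/2050 + 1/4100) = 0.293, so SE = 0.541 mmHg.

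Added variance: 2s²/G.

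SE ratio: r = √(1 + (2s²/G)/0.293).

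Actual false-positive rate at nominal 5%: 2 × [1 − Φ(1.96/r)].

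| G | s (mmHg) | 2s²/G | r | False-positive rate |
|---|---|---|---|---|
| 60 | 0 | 0 | 1.000 | 5.0% |
| 60 | 0.5 | 0.008 | 1.014 | 5.3% |
| 60 | 1 | 0.033 | 1.055 | 6.3% |
| 60 | 2 | 0.133 | 1.206 | 10.4% |
| 20 | 0 | 0 | 1.000 | 5.0% |
| 20 | 0.5 | 0.025 | 1.042 | 6.0% |
| 20 | 1 | 0.100 | 1.158 | 9.1% |
| 20 | 2 | 0.400 | 1.538 | 20.3% |

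At SD 20, s = 2 is 4/400 = 1% of the total variance. A separate calculation by variance share, with 3% of variance between residents and groups, gives ratios of 1.21 (G = 60) and 1.55 (G = 20) at 1%, in agreement with the table.

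The department term lists only Family Medicine and Medicine. If nurse practitioner trainees are not in this model, G would be 5 × 2 × 4 = 40. At s = 2 the added variance is 0.200, r = 1.297 and the rate is 13.1%, which lies between the two cases.

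**The case against.** **Randomisation by group covers one year.** This stands. Schedulers assigned trainees afterwards, the data are analysed as a cohort study, and no separate randomised year-1 comparison is planned. For the full data set the argument rests on group delivery and shared dates, which matter in a cohort study too.

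**Study cohort might already be the training group.** The term is undefined, and the separate department term counts against reading it as specialty. But the Trial Design section places groups of trainees within specialty cohorts, so reading it as training group is strained. Even on that reading, an effect for cohort that is not crossed with period would not supply the term that matters.

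**The size is not known.** This stands. The documents give no group-by-period variance, and at zero there is no error. An s of 2 mmHg means that groups' true changes differ with SD √2 × 2 = 2.8 mmHg, close to the whole 3 mmHg target, so it is a high value. The counts of 60 and 20 carry the year-1 structure into years when it was not maintained, and pair four years of groups with readings planned for three.

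**Groups are not clean units.** Some components were done individually, and alternative dates mixed attendance. A reader might infer that the number of independent units is simply the number of groups. The documents do not support that, because the contrast is within resident and the within-group correlation of change is unknown.

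**Conclusion.** The point holds in conditional form. Training was delivered in groups, and no reading of the Statistical analysis section includes a training-group-by-period term. If before/after changes are correlated within groups, the standard error is understated: by a factor of up to 1.2 with 60 groups and 1.5 with 20 shared dates, for an assumed group-by-period SD of up to 2 mmHg and total SD of 20 mmHg. The false-positive rate then runs from 5% to 10%, or from 5% to 20%. If changes are not correlated, the planned inference is unaffected on this point.

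A reader might go further and conclude that the standard error is too small as a matter of fact, because the randomised unit is missing from the model. The documents do not support that. Randomisation by group was confined to year 1, a missing group intercept has almost no effect on this contrast, and the variance that would do the damage is not given.

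**What to change.** In the Statistical analysis section:

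1. Define study cohort.
2. Add a random effect for training group by period, alongside the resident effect. Alternatively, use a cluster-robust variance at training-group level with a small-sample correction. A group intercept alone is not enough.
3. Define the training group by the session attended, so that trainees who used an alternative date belong to that session, and say how membership is set when a trainee's two sessions were with different groups.
4. Report the number of training groups in each year and the estimated group-by-period variance.

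The cost is a wording change, a re-run of the models, recovery of a session identifier for each trainee, and somewhat wider confidence intervals if the variance is not negligible. The Data Management section does not list a session identifier, so its availability has to be confirmed.

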### **Setting**

This trial is being conducted at a single academic safety net hospital system that includes clinical delivery sites at the academic medical center, a community hospital, and three outpatient centers. Approximately 40% of medical center's primary care patients are low income and ~27% non-white. The surrounding community includes 34% of residents that do not speak English at home, 21% are Hispanic/Latinx, and there are large newcomer immigrant and refugee populations. The medical center is a major regional training site for medical students, graduate nursing students, and postgraduate medical residents. The participating training programs include the internal medicine (IM), family medicine (FM) residency training programs, and the Doctor of Nursing Practice (DNP) nurse practitioner graduate school program. Participant recruitment started in September 2018 and we will enroll trainees and patients until August 2021. Data collection will continue until November 2021.

**Version 3.0 updates:** Participant recruitment started in September 2018 and continued until we will enroll trainees and patients until August 2022. Data collection continued until December 2022.

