#### Patient Measures

The primary trial outcome is the change in BP as reported in the EMR. Clinical measurements are collected in the 15-week control period prior to CONSULT-BP training period and during a 20-week post intervention period. The *main outcome* measures in the primary analysis will be systolic and diastolic BP (mm Hg) from the EMR. Analyses will stratify BP control as defined by the Joint National Commission 8: controlled HTN defined as SBP of <140/90 for most patients, or SBP < 150/90 for patients  $\geq 60$  years without a diagnosis of diabetes or chronic kidney disease, and uncontrolled hypertension as defined as greater than these values.

**Version 3.0 updates:** The original study design also included secondary patient self-reported outcomes including adherence to visits, diet modification and antihypertensive medication use as measured by the BP Self-Care Scale, Hypertension Medication Nonadherence Scale, and quality of communication and trust measured in the Health Care Climate Questionnaire and the trust sub-scale of the Primary Care Assessment Survey. In year 1, these surveys were administered in clinic offices of participating trainees in the 15-weeks before and 20-week after the educational intervention. This was not possible after the first year of the trial due to the COVID emergency.

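### Chronic kidney disease is left out of the adjustment set although the plan needs it to classify BP control, so a change in its share between windows could bias the before–after effect

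*Combined protocol and SAP*

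**What the plan says.** The document is a single combined protocol and SAP.

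- **Adjustment set (Statistical analysis).** The comorbidity terms are "relevant clinical comorbidity(diabetes, obesity, hyperlipidemia, coronary artery disease, cerebrovascular disease, and tobacco use". Besides these, the models hold strata formed by race and insurance, together with "clinical department (Family Medicine vs Medicine), age and sex". These terms are said to be there for study composition and possible confounding. The models "were fit with mixed effects for resident ID and for study cohort". No patient-level effect and no site term are listed.
- **Cut-off (Patient Measures).** Control means below 140/90 for most patients. The 150/90 limit applies to patients of at least 60 "years without a diagnosis of diabetes or chronic kidney disease".
- **Outcomes.** The main outcome "measures in the primary analysis will be systolic and diastolic BP (mm Hg) from the EMR" is continuous. The binary analyses are "logit models for normal and optimal BP categories", and the plan does not define those two categories.
- **Design (Trial Design; Intervention Assignment and Recruitment; Statistical analysis).** Randomised training dates were kept only in the first year. After that, programme schedulers placed trainees by availability, and the data are analysed as a cohort study.
- **Sites (Setting).** The hospital system "includes clinical delivery sites at the academic medical center, a community hospital, and three outpatient centers".

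**The concern.** Two diagnoses settle which cut-off applies to a patient aged 60 or over. One of them, diabetes, is in the model and the other is not, and no reason is given. For a patient of that age without diabetes, control cannot be classified unless CKD status is known, so the variable must be available.

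This matters more because of the design. Without randomised dates, the effect rests on comparing patients seen before training with patients seen after it, and the listed covariates are the main stated protection against differences between those two groups. Nothing says that the same patients appear in both windows: the sample size section counts 10 before and 20 after per trainee. If CKD patients make up a different share after training, and their BP differs from that of otherwise similar patients, the difference is credited to training. The bias could go either way.

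**Working it through.** **1. The plan's own yardstick.** The sample size section claims more than 90% power for 3 mmHg with 2050 observations before and 4100 after (all hypertension), or 1025 and 2050 (uncontrolled). It gives no SD and no intracluster correlation, so the power cannot be reproduced exactly. Taking two-sided 5% and independent observations, the largest SD that gives 90% power is 3 / [(1.960 + 1.282) × √(1/n₁ + 1/n₂)].

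- All hypertension: 3 / (3.242 × 0.02705) = 34.2 mmHg.
- Uncontrolled: 3 / (3.242 × 0.03826) = 24.2 mmHg.

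The claim is consistent with SDs below these values before any clustering. Only the 3 mmHg is used below.

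**2. Does the resident effect deal with CKD?** A resident intercept is the same in both windows. It takes out differences between residents, including part of a shift that arises because some residents contribute relatively more patients in one window. It does not take out a change in the CKD share of one resident's own patients. A cohort effect likewise leaves changes within a cohort in place.

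**3. Size on the mmHg scale.** Bias ≈ (change in CKD share between windows) × (BP difference for CKD), both conditional on the terms already in the model. The documents give neither input. Assumed values, result in mmHg:

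| BP difference | 2-point shift | 5-point shift | 10-point shift |
|---|---|---|---|
| 2 mmHg | 0.04 | 0.10 | 0.20 |
| 5 mmHg | 0.10 | 0.25 | 0.50 |
| 10 mmHg | 0.20 | 0.50 | 1.0 |

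Against 3 mmHg, the range is 0.04/3 = 1% to 1.0/3 = 33%, and the middle case is 0.25/3 = 8%. Producing the full 3 mmHg would need a shift of 3/10 = 30 points or 3/5 = 60 points.

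**4. Size on the control scale.** This concerns only patients aged 60 or over without diabetes. With assumed SBP mean 140 and SD 18, P(SBP < 150) = Φ(10/18) = 0.71 and P(SBP < 140) = 0.50, a gap of 0.21. Over means 135 to 145 and SDs 15 to 20, the gap is 0.18 to 0.26. A 5-point CKD shift in this group therefore moves its controlled share by 0.9 to 1.3 points with no change in BP. This uses the systolic limit alone; the shared diastolic limit is ignored.

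**5. Site.** This was simulated with no true effect: 205 residents, nominally 10 patients before and 20 after each, sites 5 mmHg apart, patient SD 18, resident SD 2, 40 replicates.

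- Residents fixed at one site, 11-point shift from unequal patient numbers: bias 0.55 mmHg without a resident effect (5 × 0.11 = 0.55) and 0.30 with a random resident intercept.
- Residents rotating, 10-point shift: bias 0.60 mmHg with or without the resident effect. Direct arithmetic gives 5 × 0.10 = 0.5. The gap is within simulation error, which is about 18 × 0.02705 / √40 = 0.08.

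**The case against.** The strongest reply is that any variable missing from an observational model could confound, and this plan already adjusts for six comorbidities, age, sex, department and race/insurance strata, with resident and cohort effects. Several parts of that reply stand.

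- **No shift is documented.** A reader might infer that case mix is known to have changed between windows. Nothing in the documents reports a change in CKD share or in site mix. They show a route to confounding, not an observed imbalance.
- **The cut-off does not touch the primary outcome.** A reader might carry the 140-versus-150 argument over to the main analysis. That outcome is continuous SBP and DBP, where CKD is an ordinary candidate confounder. The modelled binary categories are undefined and may not be the control definition in Patient Measures.
- **Site is weaker than CKD.** The list of delivery sites describes the hospital system. It does not say that trainees' hypertension patients come from all of them, that residents rotate, or that site was extracted. Resident, cohort and department terms can absorb part of a site difference.
- **The CKD difference may be small.** Age, diabetes, obesity and vascular disease are already in the model, so the remaining difference may lie at the low end of the assumed range.

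The Patient Enrollment exclusion for other serious comorbidity that interferes with hypertension self-control might remove some severe CKD. It does not settle the matter: CKD is not named there, and a cut-off rule that mentions CKD presupposes that such patients are in the analysis.

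**Conclusion.** The point holds for CKD, and it is modest. A covariate that the plan must obtain for its own control definition is missing from models that rely on covariates for comparability, and the resident effect does not cover a change within a resident's panel. Under assumed inputs the bias is about 0.25 mmHg, with a range of 0.04 to 1.0, against a 3 mmHg target. CKD alone would not plausibly create an effect of the design size. The figures rest on the assumed shift and the assumed conditional BP difference, neither of which is in the documents.

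It is tempting to add 0.25 mmHg for CKD to 0.5 mmHg for site and report 0.75 mmHg, a quarter of the target. The documents do not support that sum. It requires two undocumented shifts acting in the same direction and gives the resident effect no credit. Site remains a conditional question that the plan can answer with one sentence or one model term.

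**What to change.** 1. Add CKD to every adjusted model in the Statistical analysis section. Define it for each patient by the same look-back before the visit in both windows, and state that the other comorbidities follow the same rule. Status recorded only up to the training date would not serve: patients first seen afterwards may have no earlier record, so comorbidity would be under-recorded in the later window alone.
2. Tabulate CKD by window, so that a shift can be seen rather than assumed. Use the windows that the models use; the plan gives 6 months in Statistical analysis but 15 and 20 weeks in Patient Measures.
3. The section is written in the past tense. If models are already fitted, report the CKD-adjusted estimate beside the estimate from the listed covariates and label it as added later.
4. Secondary: if visit site is in the EMR extract, and residents see patients at more than one site or site mix differs by window, add a fixed effect for site. Otherwise state that residents stay at one site.

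The cost is one model term for CKD, a few more if site is added, and one table. CKD status is already needed for the control classification; whether site was extracted has to be checked.
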